Research strategy general considerations: Administration of ADV/HSV-tk + Valacyclovir in combination with SBRT before nivolumab represents a novel window of opportunity to enhance nivolumab efficacy by boosting endogenous immune-mediated antitumor activity and neoantigen expression. The aims of this study are to assess the efficacy, safety, and toxicity of this new therapeutic approach. This study will also provide a deeper understanding of the immune response and abscopal effect elicited by this therapeutic approach.

4. Objectives and endpoints

Primary Objective:

- To determine the ORR of ADV/HSV-tk + Valacyclovir therapy in combination with SBRT used as a window of opportunity treatment before nivolumab in patients with metastatic squamous or non-squamous NSCLC and metastatic uveal melanoma. Both RECIST 1.1 and modified immune-related response criteria (irRC; derived from RECIST 1.1) will be used to assess treatment response (See Appendix D).

Secondary Objectives:

- To determine the DoR of ADV/HSV-tk + Valacyclovir therapy in combination with SBRT used as a window of opportunity treatment before nivolumab in patients with metastatic squamous or non-squamous NSCLC and metastatic uveal melanoma.
- To determine the OS rate of ADV/HSV-tk + Valacyclovir therapy in combination with SBRT used as a window of opportunity treatment before nivolumab in patients with metastatic squamous or non-squamous NSCLC and metastatic uveal melanoma.
- To determine the PFS rate of ADV/HSV-tk + Valacyclovir therapy in combination with SBRT used as a window of opportunity treatment before nivolumab in patients with metastatic squamous or non-squamous NSCLC and metastatic uveal melanoma.
- To document the toxicities associated with ADV/HSV-tk + Valacyclovir therapy in combination with SBRT used as a window of opportunity treatment before nivolumab in patients with metastatic squamous or non-squamous NSCLC and metastatic uveal melanoma, as assessed by the National Cancer Institute (NCI) Common Terminology Criteria for Adverse Events (CTCAE) v4.03.
- To document the antitumor activity of ADV/HSV-tk + Valacyclovir therapy in combination with SBRT used as a window of opportunity treatment before nivolumab in patients with metastatic squamous or non-squamous NSCLC and metastatic uveal melanoma, as assessed by both RECIST 1.1 and modified irRC (See Appendix D).

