- To estimate the clinical benefit rate (CBR) of ADV/HSV-tk + Valacyclovir therapy in combination with SBRT used as a window of opportunity treatment before nivolumab in patients with metastatic squamous or non-squamous NSCLC and metastatic uveal melanoma.

Exploratory Objectives:

- To determine the abscopal effect of ADV/HSV-tk + Valacyclovir therapy in combination with SBRT. The primary criterion for abscopal effect evaluation will be computed tomography (CT)-based response assessment of a non-targeted lesion. The secondary criterion will be immune parameters including PD-1 and PD-L1 expression, immune infiltrates, and cytokine expression (IL-1, IL-2, IL-6, IL-12, IFN- γ , TNF- α , and GM-CSF).
- To measure the immune response to nivolumab in patients with squamous or non-squamous NSCLC and metastatic uveal melanoma.
- To assess the Th1 (cellular-based) response by measuring the following cytokines: IL-1, IL-2, IL-6, IL-12, IFN- γ , TNF- α , and GM-CSF.
- To measure TILs before and after ADV/HSV-tk + Valacyclovir therapy.
- To explore correlative tissue and blood-based biomarkers of treatment response including but not limited to T-cell cytokine profiles (IL-1, IL-2, IL-6, IL-12, IFN- γ , TNF- α , and GM-CSF), TILs, PD-1 and PD-L1 expression, effector and suppressor immunocyte populations.

Endpoints

Primary endpoint: The primary endpoint will be the ORR of ADV/HSV-tk + Valacyclovir therapy in combination with SBRT used as a window of opportunity treatment before nivolumab in patients with metastatic squamous or non-squamous NSCLC and metastatic uveal melanoma. Both RECIST 1.1 and modified irRC will be used to assess treatment response.

Secondary endpoints: Secondary endpoints will include a) DoR; b) OS and PFS rates; c) CBR; d) safety and toxicity (toxicity will be defined as any treatment-related death or any \geq Grade 3 toxicity excluding alopecia and constitutional symptoms as assessed by NCI CTCAE v4.03); e) immune-mediated antitumor activity (assessed by RECIST 1.1 and modified irRC); and f) correlative tissue and blood-based biomarkers of ADV/HSV-tk + Valacyclovir therapy in combination with SBRT used as a window of opportunity treatment before nivolumab.

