Patients whose treatment is interrupted or permanently discontinued due to an AE including abnormal laboratory value must be followed at least once a week for 4 weeks and subsequently at 4-week intervals until resolution or stabilization of the event, whichever comes first. Dose interruptions should be reported on the appropriate Dosage Administration case report form (CRF). The maximum time allowed for toxicity-related treatment interruption is 21 days (3 weeks) from the intended dosing day. If interruption is > 3 weeks, the patient must be discontinued from the study treatment. However, the patient will continue to be followed for toxicity.

7. Population

Metastatic NSCLC: Male or female patients aged ≥ 18 years with histologically or cytologically confirmed metastatic squamous or non-squamous NSCLC whose disease has progressed after a platinum-based chemotherapy and after a single-agent immunotherapy. Patients with *EGFR* or *ALK* genomic tumor aberrations should have disease progression on FDA-approved therapy for these aberrations prior to receiving nivolumab. The investigator or designee must ensure that the patient meets all the inclusion and none of the exclusion criteria before being offered enrollment in the study.

Metastatic Uveal Melanoma: Male or female patients aged ≥ 18 years with histologically or cytologically confirmed metastatic uveal melanoma that is immunotherapy naïve.

Study Duration:

After administration of ADV/HSV-tk + Valacyclovir followed by SBRT, nivolumab will be given every 4 weeks from day 17 until disease progression, unacceptable toxicity, or up to 12 months in patients without disease progression. Patients will be followed up for 6 months or until disease progression, whichever occurs first. Patients will be assessed for AEs up to and including 30 days after the last treatment dose.

Safety Criteria:

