14.2 Reporting

The principal investigator has the obligation to promptly report all patient deaths and related and unexpected AEs and SAEs to the local IRB and FDA. To ensure patient safety, every related SAE (as per principal investigator determination) occurring:

- after the patient has provided informed consent up to and including 30 days after the last treatment dose
- after protocol-specified procedures begin and 30 days after the patient has stopped study treatment
- after the start of any period in which the study protocol interferes with the standard medical treatment given to a patient up to and including 30 days after the patient has stopped study treatment must be reported to the local IRB within 24 hours of learning of its occurrence; this includes serious, related, labeled (expected) and serious, related, and unlabeled (unexpected) adverse experiences. All deaths up to and including 30 days after the last treatment dose following completion of the active protocol therapy must be reported within 5 working days.

Recurrent episodes, complications, or progression of the initial SAE must be reported as follow-up to the original episode within 24 hours of the investigator receiving the follow-up information. A SAE occurring at a different time interval or otherwise considered completely unrelated to a previously reported one should be reported separately as a new event. The end date of the first event must be provided.

Each reoccurrence, complication, or progression of the original event should be reported as a follow-up to that event regardless of when it occurs. The follow-up information should describe whether the event has resolved or continues, if and how it was treated, whether the blind was broken or not (if applicable), and whether the patient continued or withdrew from study participation.

The investigator should inform the IRB of the occurrence of any SAEs not previously documented in the Investigator Brochure or Package Insert (new occurrence) and thought to be related to the study drug. The

Investigator and the local IRB may need to issue an Investigator Notification to inform all investigators involved in any study with the same drug that this SAE has been reported. Suspected unexpected serious adverse reactions will be collected and reported to the competent authorities. The following categories and definitions of causal relationship to study drug should be considered for use in this clinical study:

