Statistical Analysis: DoR, OS, PFS, and CBR will also be analyzed. Safety profiles will be assessed through summaries of AEs, SAEs, AEs leading to treatment discontinuation, and treatment-related death. The safety analysis will report the frequency of all AEs and laboratory abnormalities as well as the frequency of dose interruptions and toxicity-related treatment discontinuation. Toxicity rates will be presented using the worst NCI CTCAE grade per patient.

Data Management: CRFs will be designed and utilized to capture all patient data. An electronic database will be designed to store patient CRFs. Data quality control will be performed regularly by the research coordinator/research nurse to ensure timely, accurate, and complete patient data collection. Queries will be generated and resolved prior to generation of interim and final summary reports.

16 Protocol amendments or changes in study conduct

Any change or addition to this protocol requires a written protocol amendment that must be reviewed by the investigator, local IRB, and FDA before implementation. Amendments significantly affecting the safety of subjects, the scope of the investigation, or the scientific quality of the study require additional approval by the IRB at each study center and the FDA. Examples of amendments requiring such approval are:

1. Increases in drug dose or duration of exposure of subjects
2. Significant changes in the study design (e.g., addition or deletion of a control group)
3. Increases in the number of invasive procedures
4. Addition or deletions of a test procedure required for safety monitoring

These requirements for approval should in no way prevent any immediate action from being taken by the investigator in the interests of preserving the safety of all patients included in the trial. The IRB must be notified if immediate changes are made to the protocol by the investigator for safety reasons. Amendments affecting administrative aspects of the study do not require formal protocol amendments but will require IRB approval.

17 Data safety monitoring

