UPIRSOs, noncompliance, and protocol deviations/violations that affect the scientific integrity of the study, subject rights, or subject welfare and safety must be promptly reported to the IRB via MORTI according to the table below. Events that do not require prompt reporting should be summarized and reported to the IRB at the time of continuing review in answer to the question about study progress. If, on review, the Investigator notes a trend in AEs or protocol deviations that would affect the study as a whole, this should be reported to the IRB as an UPIRSO.

HMRI IRB Reportable Events Deadlines	
Event	Deadline
UPIRSO	7 calendar days
UPIRSO involving a death, or life-threatening event of a HMRI participant, or a participant at a site that relies on the Houston Methodist Hospital MH as a Coordinating Center	24 hours May be initiated by email but must be submitted first following business day
Noncompliance	When aware
Protocol Deviation (non-emergency)	7 working days
Protocol Deviation (emergency)	5 working days

III. Data Quality and Safety Review Plan and Monitoring

A. Data Quality and Management

- Description of Plan for Data Quality and Management:** The PI or study staff will review all data collection forms on an ongoing basis for data completeness and accuracy as well as protocol compliance.
- Frequency of Data Review for this Study:** Study data will be reviewed by the PI quarterly as follows:

Data type	Frequency of review	Reviewer
Subject accrual (including compliance with protocol enrollment criteria)	Quarterly	PI, Independent Monitor(s)
Status of all enrolled subjects, as of date of reporting	Quarterly	PI, Independent Monitor(s)

Adherence data regarding study visits and intervention	Quarterly	PI, Independent Monitor(s)
AEs and rates (including out-of-range lab values)	Quarterly	PI, Independent Monitor(s)
SAEs	Per occurrence	PI, Independent Monitor(s), FDA (if applicable)

B. Subject Accrual and Compliance

1. Measurement and Reporting of Subject Accrual and Compliance with Inclusion/Exclusion Criteria

Review of the rate of subject accrual and compliance with inclusion/exclusion criteria will occur monthly during the 4-month recruitment phase and then every 3 months to ensure that a sufficient number of participants are being enrolled and that they meet eligibility criteria.

2. Measurement and Reporting of Participant Adherence to Treatment Protocol

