Data on adherence to the treatment protocol will be collected twice weekly by research staff and reviewed quarterly by the PI, the study statistician, and the safety officer. Adherence of participants will be evaluated by performing pill counts and by monitoring the appropriate case report form intake data measures at each visit.

C. Stopping Rules

This study will be stopped prior to its completion if: (1) the intervention is associated with adverse effects that call into question the safety of the intervention; (2) difficulty in study recruitment or retention will significantly impact the ability to evaluate the study endpoints; (3) any new information becomes available during the trial that necessitates stopping the trial; or (4) other situations occur that might warrant stopping.

D. Safety Review Plan

Study progress and safety will be reviewed quarterly (and more frequently if needed). Progress reports, including patient recruitment, retention/attrition, and AEs will be provided to the Independent Monitor(s) following each of the quarterly reviews. An Annual Report will be compiled and will include a list and summary of AEs. In addition, the Annual Report will address (1) whether AE rates are consistent with pre-study assumptions; (2) reason for dropouts from the study; (3) whether all participants met entry criteria; (4) whether continuation of the study is justified on the basis that additional data are needed to accomplish the stated aims of the study; and (5) conditions whereby the study might be terminated prematurely. The Annual Report will be sent to the Independent Monitor(s) and will be forwarded to the IRB (if applicable), FDA, and Sponsor. The IRB and other applicable recipients will review study

progress on an annual basis.

E. Study Report Outline for the Independent Monitors(s) (Interim or Annual Reports)

Study Report tables will be generated only from aggregate (not by group assignment) baseline and aggregate safety data for the study population. A separate Closed Safety Report, with masked group baseline and safety data, will be generated for the Independent Monitor(s) by a designated unmasked member of the team but will not be reviewed by the study team.

IV. Informed Consent

Written informed consent will be obtained from each subject at entry into the study. Informed consent is obtained by the following process:

1. The subject (If applicable, parent/guardian) will be asked to review the study consent form.

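### Overall survival is a secondary endpoint, but the text schedules no vital-status contact after progression, so OS is open to incomplete ascertainment and informative censoring

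*Combined protocol and SAP*

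**What the plan says.** Section 4 lists among the secondary objectives "To determine the OS rate of ADV/HSV-tk + Valacyclovir therapy in combination with SBRT" and among the secondary endpoints "b) OS and PFS rates". No time point is attached to the rate. On analysis, Section 15 says only "DoR, OS, PFS, and CBR will also be analyzed", without a time origin, estimator, censoring rule or data cut-off.

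Section 7 (Study Duration) gives the follow-up rule: "Patients will be followed up for 6 months or until disease progression, whichever occurs first". It does not say when the 6 months begin. The visit schedule in Section 11 has no column after end of treatment.

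Several places could still bring in information after progression:

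- **Death reporting.** Section 14.2 states "The principal investigator has the obligation to promptly report all patient deaths". Section 7 (Safety Criteria), the Section 11 footnotes and Section 12 also ask for any patient's death to be reported, with no time limit. The one death deadline tied to a period covers "All deaths up to and including 30 days after the last treatment dose following completion of the active protocol therapy".
- **Withdrawal reasons.** Section 12.4 lists loss to follow-up and death as separate reasons, to be recorded in the CRF. Progression is not on that list.
- **Quarterly review.** Section 17 III.A includes "Status of all enrolled subjects, as of date of reporting", with status undefined. The progress report content named in III.D is recruitment, retention or attrition, and adverse events.
- **Limited further observation.** There is a tumor assessment 30 days after the last nivolumab dose (Section 4), a Safety Follow-up Visit (mentioned in 13.1.1), follow-up of adverse events that interrupted or ended treatment (Section 6), and possible treatment beyond confirmed immune-related progression (12.3).
- **Glossary.** Survival follow-up appears once, as a condition within a definition.

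**The concern.** OS needs every patient's vital status up to a defined date. Here planned follow-up ends at an event that is itself related to the risk of death. After that, a death enters the data if someone reports it, while a survivor generates no report at all.

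Two errors can follow. If later deaths go unreported and patients are censored near progression, OS tends to look too long. If later deaths are reported but survivors stay censored near progression, OS can look too short. The text does not settle which would dominate. With 9 and 16 patients, a few unknown statuses can move the estimate materially.

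The gap is not confined to progression. Section 12.4 withdraws patients from treatment and procedures for several toxicities and makes no exception for survival contact.

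**Working it through.** **1. The plan's own figures.** The only stated power figures are for response rate (Section 15.1). The exact binomial upper tail P(X ≥ r | n, p) gives:

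- NSCLC, n = 16, r = 3: power 0.803 at 25%, alpha 0.011 at 3%.
- Uveal melanoma, n = 9, r = 2: power 0.804 at 30%, alpha 0.028 at 3%.

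These match the stated 80.3% and 80.4%, and nothing below changes them. The documents give no event count or precision for OS.

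**2. Inputs for an illustration (Section 1.1).** Uveal melanoma on anti-PD-1/PD-L1: median PFS 2.6 and OS 7.7 months. Non-squamous NSCLC on nivolumab: median PFS 2.3 and OS 12.2 months. The NSCLC source did not require prior immunotherapy, as this trial does, so neither pair is a forecast.

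**3. Alive after progression at 6 months.** Assume S(t) = exp(−ln 2 × t/median). Everyone progression-free is alive, so the share is S_OS(6) − S_PFS(6).

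| | S_OS(6) | S_PFS(6) | PFS event by 6 months | Alive after progression |
|---|---|---|---|---|
| Uveal, n = 9 | 0.583 | 0.202 | 79.8% (7.2) | 0.381 (3.4) |
| NSCLC, n = 16 | 0.711 | 0.164 | 83.6% (13.4) | 0.547 (8.8) |

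With Weibull shapes from 0.7 to 1.5 (assumed), varied separately for PFS and OS, the shares run 27–53% and 40–73%.

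**4. Allowing for continued observation.** Section 12.3 requires confirmation of immune-related progression at least 6 weeks later (about 1.4 months). Suppose observation lasts that long, and then also 30 days more (about 1 month). The share alive at month 6 but past observation is at least S_OS(6) − S_PFS(6 − lag).

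- Lag 1.4 months: uveal 0.583 − 0.293 = 0.29; NSCLC 0.711 − 0.250 = 0.46.
- Lag 2.4 months: uveal 0.583 − 0.383 = 0.20; NSCLC 0.711 − 0.338 = 0.37.

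These are lower bounds, because some patients who were progression-free at the earlier time die before month 6.

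**5. Direction of bias.** A simulation of 400,000 patients per scenario used the same medians. It assumed exponential PFS and post-progression survival, 5–20% of PFS events being deaths, and an 18-month horizon (12 months of treatment plus 6). Kaplan-Meier OS at 12 months was:

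| | True | Censored 0–1 month after progression | 50–80% of later deaths reported, others censored 1 month after progression |
|---|---|---|---|
| Uveal | 0.28–0.30 | 0.45–0.85 | 0.25–0.29 |
| NSCLC | 0.51 | 0.49–0.83 | 0.33–0.40 |

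Expected deaths by 18 months with full follow-up are 7.7–8.0 of 9 and 10.2–10.8 of 16. If observation stops 0–1 month after progression, 0.4–2.7 and 0.8–3.9 would be seen.

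**6. Precision.** Even with complete data OS will be imprecise. Hypothetical exact 95% intervals are 7–70% for 3 of 9 alive and 25–75% for 8 of 16.

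**The case against.** The best defence is that the protocol is not blind after progression. Deaths are reportable without a time limit, and loss to follow-up and death are distinct CRF entries. Progression is not a withdrawal reason, and subject status is reviewed every quarter. Section 12 also refers to further schedules in a study manual, the CRFs are still to be designed (Section 15), and the design figure is not visible. With at most 25 patients, missing dates might be recovered from records before database lock.

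Much of this stands, and it rules out several stronger readings that a reader might draw:

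- *Deaths after progression are not collected.* The text asks for them in several places.
- *A patient without a death report cannot be told apart from one lost to contact.* Section 12.4 records these separately, so this is too strong. What is missing is scheduled contact that would make the entries reliable and dated.
- *The glossary ends follow-up.* It is generic, mentioning randomization and placebo in a single-arm trial, and is weak evidence either way.
- *The loss could not be repaired later.* Records might supply dates, although the plan does not provide for that search.
- *Follow-up has ended for all of the 38% and 55%.* Step 4 of the working shows the share beyond observation could be much smaller.

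The defence does not supply a contact schedule, a last-known-alive date, or a definition of status that includes vital status. Those gaps in the text remain.

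**Conclusion.** The point holds as a risk to a secondary endpoint. Followed as written, the plan commits to OS without scheduling the contact that OS needs, and passive death reporting does not reliably cover survivors.

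A reader might infer that the OS estimate will be biased, or biased upward. The documents do not support that. The simulated estimates fell on both sides of the truth, and in one NSCLC scenario 12-month OS was nearly unbiased (0.49 against 0.51) although most deaths were missed.

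The illustrative size is 38% (uveal) and 55% (NSCLC) alive after progression at 6 months, or as little as about 20% and 37% beyond observation under the longer lag. These rest on medians from other populations and exponential times; the gap in the text does not depend on them. How serious it is in practice depends on what the site collects, which the text leaves open. OS is unpowered, and the primary analysis and sample size stand.

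**What to change.** Keep the Section 7 sentence for PFS and duration of response, and state when its 6 months begin. Then add:

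1. **Contact.** For all patients, regardless of progression or treatment discontinuation and unless consent for follow-up is withdrawn, check vital status by telephone or record review every 3 months until death or a common data cut-off. Time the checks with the quarterly status review.
2. **Final sweep.** At the cut-off, confirm each survivor's status. Without this, reported deaths would still be set against survivors censored early.
3. **Cut-off.** One option is 18 months after the last patient's day 17, which allows 12 months of nivolumab plus 6 months: 17 + 365 + 183 = about day 565 for that patient.
4. **CRF.** Record the date of death or the last-known-alive date.
5. **Analysis.** Estimate OS from day 0 by Kaplan-Meier at a prespecified landmark. Ignore deaths after the cut-off. Censor survivors at the cut-off, or at last known alive only if truly lost.
6. **Consistency.** Define status in Section 17 III.A to include vital status. Reconcile the glossary and Sections 7, 12.3, 12.4, 14.2 and 17 on when follow-up ends, including which response criteria define the progression that ends it.

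The cost is a protocol amendment with IRB and FDA review, a possible consent update, one or two CRF fields, a few calls or record checks for at most 25 patients, and a later final OS report. No scans or clinic visits are added.
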